### Bristol Stool Chart

Type 1		Separate hard lumps, like nuts (hard to pass)
Type 2		Sausage-shaped but lumpy
Type 3		Like a sausage but with cracks on its surface
Type 4		Like a sausage or snake, smooth and soft
Type 5		Soft blobs with clear-cut edges (passed easily)
Type 6		Fluffy pieces with ragged edges, a mushy stool
Type 7		Watery, no solid pieces. Entirely Liquid

## APPENDIX B. GASTROINTESTINAL SIGNS AND SYMPTOMS CHECKLIST

The following signs and symptoms checklist will be reviewed each day starting with Day 1 after dosing, and then on Days 2, 3, and 7. Presence or absence of each sign or symptom will be recorded and if appropriate, an AE will be reported. With respect to laboratory tests and FOBT, criteria for clinical significance are provided and a yes/no response is required. If any of these are present prior to study drug administration, they will be reported with other medical history. The severity of the AEs will be in accordance with the FDA's Toxicity Grading Scale for Healthy Adult and Adolescent Volunteers Enrolled in Preventive Vaccine Clinical Trials.

Signs/Symptom	Present? (circle yes or no)
Epigastric pain/discomfort (dyspepsia)	Yes / No
Fatigue	Yes / No
Light headedness	Yes / No
Postural dizziness	Yes / No
Syncope	Yes / No
Nausea	Yes / No
Vomiting	Yes / No
Hematemesis (vomiting blood)	Yes / No
Change in color of stool (melena)	Yes / No
Hematochezia (anal or rectal bleeding)	Yes / No
Clinically Significant Changes in Laboratory Tests	Yes / No
Positive FOBT	Yes / No
Decrease in hematocrit of at least 10 percentage points	Yes / No
Decrease in hemoglobin by at least 2 g/dL	Yes / No
Increase in BUN $\geq$ 40 mg/dL	Yes / No
Increase in creatinine $\geq$ 1.8 mg/dL	Yes / No
Increase in ALT $\geq$ 3 ULN	Yes / No
Increase in AST $\geq$ 3 ULN	Yes / No

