## **8.13. Subject and Study Discontinuation and Stopping Criteria**

### **8.13.1. Discontinuation of Individual Subjects**

Each subject has the right to withdraw from the study at any time. In addition, the investigator may discontinue a subject from the study at any time if the investigator considers it necessary for any reason, including the occurrence of an AE or noncompliance with the protocol. Subjects who withdraw from the study will not be replaced unless it is mutually agreed upon, in writing, between the investigator and the sponsor.

Some specific considerations for replacement of subjects include:

1. If a subject is considered eligible for the study but does not receive any investigational product, another subject will be enrolled to ensure that each cohort has the target number of subjects.
2. If a subject is randomized to the active group but withdraws from the study before the Day 3 clinic release procedures are performed, then a replacement subject may be considered.
3. If a subject for some reason is missing safety measures such as clinical laboratory assessments, vital signs, or FOBT.
4. If a subject for some reason is missing blood samples for PK measurements such that PK cannot be determined.

If a subject withdraws or is discontinued from the study, the reason(s) for the discontinuation from the study will be recorded and a physical examination, body weight, vital signs measurement, ECG, laboratory analyses, Stool Consistency Questionnaire, GI Symptoms Checklist, and AEs will be performed as soon as possible after discontinuation from the study. Additional blood samples for drug measurement may be collected at the time of discontinuation from subjects who are discontinued due to AEs; the clock time, and date the sample was taken will be recorded.

If a subject is discontinued from the study with an ongoing AE or an unresolved laboratory result that is significantly outside of the reference range, the investigator will attempt to provide follow-up until a satisfactory clinical resolution of the laboratory result or AE is achieved.

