#### **11.1.5. Gastrointestinal Adverse Events**

Gastrointestinal (GI) AEs will be assessed as follows:

- Stool Consistency Questionnaire – subject completed questionnaire ([Appendix A](#))
- GI Signs and Symptoms Checklist ([Appendix B](#))
- FOBT
- Open ended questions about AEs that are indicative of gastritis
- Clinical laboratory tests (hematocrit, hemoglobin, blood urea nitrogen (BUN), creatinine, ALT, and AST)
- Endoscopy (if indicated)

A-subject completed Stool Consistency Questionnaire ([Appendix A](#)) that asks 4 questions about GI symptoms will be utilized to assess GI AEs. The responses to the questions are based on a 4-point scale with 0 being no symptom and 3 being a severe symptom. The development of a new symptom or worsening of an existing symptom will be reported as an AE.

In addition, if a subject reports of any of the signs and symptoms of gastritis or potential GI ulcer complications or has a laboratory test result indicative of blood loss as shown in the GI Signs and Symptoms Checklist ([Appendix B](#)), the study gastroenterologist sub-investigator will do a thorough evaluation of the event and perform an endoscopy if it is considered warranted. A signs and symptoms checklist will be reviewed each day starting with Day 1, and then on Days 2, 3, and 7. Presence or absence of each sign or symptom will be recorded and if appropriate, a severity assessment or clinical significance evaluation will be performed.

Clinically significant changes in hematocrit and hemoglobin are defined as decreases of at least 10 percentage points and 2 g/dL, respectively. Clinically significant changes in other clinical laboratory tests will be defined as blood urea nitrogen  $\geq 40$  mg/dL, creatinine  $\geq 1.8$  mg/dL, ALT

and AST  $\geq 3$  times the upper limit of normal. If there is evidence of gastric erosion, ulcer, or bleeding in any subject confirmed by endoscopy or FOBT, the study will be stopped.

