| Repeat for Treatment, Inpatient Follow-up, Clinic Discharge, Outpatient Follow-up and Earl termination | Epigastric pain/discomfort (dyspepsia) | xx.x (xx.xx) | xx.x (xx.xx) | xx.x (xx.xx) | xx.x (xx.xx) | xx.x (xx.xx) |
| | Fatigue | xx.x | xx.x | xx.x | xx.x | xx.x |
| | Light headedness | (xx-xx) | (xx-xx) | (xx-xx) | (xx-xx) | (xx-xx) |
| | Postural dizziness | xx (xx.x%) | xx (xx.x%) | xx (xx.x%) | xx (xx.x%) | xx (xx.x%) |
| | Syncope | xx (xx.x%) | xx (xx.x%) | xx (xx.x%) | xx (xx.x%) | xx (xx.x%) |
| | Nausea | xx (xx.x%) | xx (xx.x%) | xx (xx.x%) | xx (xx.x%) | xx (xx.x%) |
| | Vomiting | xx (xx.x%) | xx (xx.x%) | xx (xx.x%) | xx (xx.x%) | xx (xx.x%) |
| | Hematemesis (vomiting blood) | xx (xx.x%) | xx (xx.x%) | xx (xx.x%) | xx (xx.x%) | xx (xx.x%) |
| | Hematochezia (anal or rectal bleeding) | xx (xx.x%) | xx (xx.x%) | xx (xx.x%) | xx (xx.x%) | xx (xx.x%) |
| | Positive FOBT | xx (xx.x%) | xx (xx.x%) | xx (xx.x%) | xx (xx.x%) | xx (xx.x%) |
| | Decrease in hematocrit of at least 10 % points | xx (xx.x%) | xx (xx.x%) | xx (xx.x%) | xx (xx.x%) | xx (xx.x%) |
| | Decrease in hemoglobin by at least 20 g/dL | xx (xx.x%) | xx (xx.x%) | xx (xx.x%) | xx (xx.x%) | xx (xx.x%) |
| | Increase in BUN \geq 40 mg/dL | xx (xx.x%) | xx (xx.x%) | xx (xx.x%) | xx (xx.x%) | xx (xx.x%) |
| | Increase in creatinine \geq 1.8 mg/dL | xx (xx.x%) | xx (xx.x%) | xx (xx.x%) | xx (xx.x%) | xx (xx.x%) |
| | Increase in ALT \geq 3 ULN | xx (xx.x%) | xx (xx.x%) | xx (xx.x%) | xx (xx.x%) | xx (xx.x%) |
| | Increase in AST \geq 3 ULN | xx (xx.x%) | xx (xx.x%) | xx (xx.x%) | xx (xx.x%) | xx (xx.x%) |

Table 5: Summary of Blood Chemistries

| | Kindolor 100 mg | Kindolor 300 mg | Kindolor xx mg | Placebo |
|--|-----------------|-----------------|----------------|-------------|
| | (N=xx) | (N=xx) | (N=xx) | (N=xx) |
| Repeat for each visit: Screening, Day -1, discharge and follow-up | | | | |
| Test Name (units) | | | | |
| N | xx | xx | xx | xx |
| Mean (SD) | xx.x (xx.x) | xx.x (xx.x) | xx.x (xx.x) | xx.x (xx.x) |
| Min - Max | xx-xx | xx-xx | xx-xx | xx-xx |
| Change from baseline at discharge and follow-up | | | | |
| N | xx | xx | xx | xx |
| Mean (SD) | xx.x (xx.x) | xx.x (xx.x) | xx.x (xx.x) | xx.x (xx.x) |
| Min - Max | xx-xx | xx-xx | xx-xx | xx-xx |

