|------------|-------|-----------|------------|---------------------------------------|-----------------------|--------------------------------|-----------------------------------|--------------------------------|-----------------------------------|
| xxxx | | Screening | mm/dd/yyyy | -30 | xxx | xxx | xxx | xx | xx.x |
| | | Day -1 | | -15 | | | | | |
| | | | | +15 | | | | | |
| | | | | +30 | | | | | |

Listing 12: GI Signs and Symptoms

| Subject ID | Group | Visit | Date | Symptoms | Present? |
|------------|-------|-----------|------------|----------|----------|
| xxxx | | Screening | mm/dd/yyyy | | |
| | | Day -1 | | | |
| | | | | | |
| | | | | | |

Listing 13: Stool Consistency

| Subject ID | Group | Visit | Date/ Time | Frequency of Stools per Day | Consistency of Stools per Day | Category/Symptom | Severity |
|------------|-------|-----------|------------|-----------------------------|-------------------------------|------------------|----------|
| xxxx | | Screening | mm/dd/yyyy | | | | |
| | | Day -1 | | | | | |
| | | | | | | | |
| | | | | | | | |

Listing 14: Plasma Concentrations

| Subject ID | Group | Nominal Timepoint | Date | Time | DCUKA (ng/mL) | 8-OH DCUKA (ng/mL) |
|------------|-------|-------------------|------------|-------|---------------|--------------------|
| xxxx | | | mm/dd/yyyy | hh:mm | xx.x | xx.x |
| | | | | | | |
| | | | | | | |
| | | | | | | |

Note: Nominal timepoints include: 15 minutes prior to dosing, then at 0.25, 0.5, 1, 1.5, 2, 4, 8, 12, 24, and 48 hours after dosing.

Listing 15: Pharmacokinetic Parameters

| Subject ID | Group | C _{max} (ng/mL) | t _{max} (hr) | AUC ₀₋₄ (h*ng/mL) | AUC ₀₋₈ (h*ng/mL) | AUC _{0-last} (h*ng/mL) | AUC _∞ (h*ng/mL) | λ _z | t _{1/2} (hr) |
|------------|-------|--------------------------|-----------------------|------------------------------|------------------------------|---------------------------------|----------------------------|----------------|-----------------------|
| xxxx | | xx.x | xx.x | xx.x | xx.x | xx.x | xx.x | xx.x | xx.x |
| | | | | | | | | | |
| | | | | | | | | | |
| | | | | | | | | | |

Listing 16: Adverse Events

| Subject ID | Treatment Group | Adverse Event (Verbatim) S: SOC P: PT Term | Start Date/ Day | Stop Date/ Day | Duration in Days | Severity | Relationship | Actions Taken | Outcome | Serious |

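### The GI Signs and Symptoms Checklist has no itemised pre-dose baseline, and it requires yes/no FOBT and laboratory answers on two days when none of those tests is scheduled

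*Protocol*

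**What the plan says.** Protocol Section 9.1 and SAP Section 3.3 list the checklist among the safety endpoints. Section 11.1.5 sets its timing: "A signs and symptoms checklist will be reviewed each day starting with Day 1, and then on Days 2, 3, and 7". Appendix B is more specific and places the first review after dosing: "reviewed each day starting with Day 1 after dosing, and then on Days 2, 3, and 7". The Schedule of Visits and Assessments has no checklist row. The checklist appears only in the footnote to the Adverse Events row, which has no Day -1 mark.

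For findings that precede dosing, Appendix B says: "If any of these are present prior to study drug administration, they will be reported with other medical history". For the FOBT and laboratory items it says: "With respect to laboratory tests and FOBT, criteria for clinical significance are provided and a yes/no response is required". The form offers only Yes and No.

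The Table 16 shell in SAP Section 12 tabulates checklist items by visit, with the instruction "Repeat for Treatment, Inpatient Follow-up, Clinic Discharge, Outpatient Follow-up and Earl termination". No pre-dose visit is named. The shell headed "Listing 12: GI Signs and Symptoms" shows Screening and Day -1 rows.

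For subjects who leave early, Protocol Section 8.13.1 states that "a physical examination, body weight, vital signs measurement, ECG, laboratory analyses, Stool Consistency Questionnaire, GI Symptoms Checklist, and AEs will be performed". FOBT is not in that list, and the FOBT row of the schedule is blank under Early Termination.

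**The concern.** Stomach toxicity is the main nonclinical finding (Protocol Section 4.9), so this checklist carries much of the symptom evidence on the most expected risk. Three features weaken it.

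- **Uneven elicitation.** Ten signs and symptoms are put to the subject individually after dosing. Before dosing there is a general history at Screening and, on Day -1, a question about whether anything has changed (Section 11.10). People tend to report more when prompted item by item, so a symptom present on both sides of the dose may be recorded only on the later side.
- **Answers without measurements.** A mandatory binary field with no test behind it invites 'No'. A 'No' from an untested subject cannot be told apart from a true negative in Table 16.
- **A gap at early termination.** The checklist and Table 16 call for an FOBT answer at a visit where the schedule provides no FOBT.

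At stake is the meaning of Table 16 and of the checklist listing, and how well a checklist symptom can be classed as treatment-emergent.

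**Working it through.** **The plan's own figure.** The only sample-size calculation is the chance of at least one AE among 6 active subjects, 1 − (1 − p)^6. For p = 0.10, 0.15, 0.20 and 0.25 this gives 46.9%, 62.3%, 73.8% and 82.2%, matching the stated 47%, 62%, 74% and 82%. The point here does not depend on it.

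**Schedules side by side** (Protocol Sections 5, 8.13.1 and 11.1.5, Appendix B, the schedule table, SAP Table 16):

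| Occasion | Checklist | FOBT | Hematology and chemistry | Visit in Table 16 |
|---|---|---|---|---|
| Screening | no | yes | yes | no |
| Day -1 | no | yes | yes | no |
| Day 1, after dosing | yes | no | no | yes |
| Day 2 | yes | no | no | yes |
| Day 3 | yes | yes | yes | yes |
| Day 7 | yes | yes | yes | yes |
| Early termination | yes | no | yes | yes |

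**Baseline.** The seven FOBT and laboratory items have a Day -1 value. The Stool Consistency Questionnaire is also given on Day -1 and covers stool frequency and consistency, urgency, abdominal pain, bloating and interference with activities. It does not ask about nausea, vomiting, fatigue, light-headedness, postural dizziness or syncope. Those items have no itemised pre-dose record.

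**Count of unmeasured answers.** The items are FOBT, hematocrit, hemoglobin, BUN, creatinine, ALT and AST, so 7. Checklist days: 4. Checklist days with no scheduled test: 2 (Days 1 and 2).

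- Scheduled answers per subject: 7 × 4 = 28
- Without a scheduled measurement: 7 × 2 = 14, or half
- All 32 subjects: 14 × 32 = 448 of 28 × 32 = 896
- The 24 active subjects: 14 × 24 = 336

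The general line on clinically significant laboratory changes also has a Yes/No field. It is left out of the count.

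**What a false zero would convey.** If all six active subjects in a dose group were entered as 'No', the cell would read 0/6. Taken as data, 0/6 gives a one-sided 95% upper limit of 1 − 0.05^(1/6) = 39.3% (two-sided 95%: 1 − 0.025^(1/6) = 45.9%). With nobody tested, the cell carries no information at all.

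**Early termination.** Six of the seven items rest on hematology or chemistry, which are scheduled at that visit. FOBT is the one that is not.

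**The case against.** A reader might infer that pre-existing symptoms will be counted as new. The documents do not support that. Appendix B sends pre-dose findings to medical history, Section 11.1.1 excludes unchanged pre-existing conditions from AEs, Section 11.1.4 does the same for laboratory values that were already abnormal and have not risen by a grade, and a checklist 'Yes' becomes an AE only where appropriate. The entry criteria also remove significant GI disease, reflux, ulcers, GI bleeding and a history of syncope or near-syncope on change of posture. What remains is narrower: the medical-history rule works only for symptoms that were elicited, and the pre-dose elicitation is weaker.

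The concurrent blinded placebo group faces the same before/after asymmetry and has its own column in Table 16. That protects the comparison between groups. It does not help to classify an individual subject's symptom. Nor would a Day -1 checklist capture effects of the overnight fast or the PK blood draws, since both come later; for those, the placebo column is the safeguard.

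It is also fair to say that 'No' entries are an inference. The eCRF is not shown, an item might be left blank, and Section 11.3 allows unscheduled laboratory samples. Table 16 does not state its percentage denominator beyond the column N. The count of 448 is a count of form fields, not of errors.

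Finally, the Screening and Day -1 rows in Listing 12 look like template text: Listings 11 and 13 have the same rows, and Listing 20 shows Weeks 4, 8 and 12. They need aligning but prove little.

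**Conclusion.** The point stands in a limited form and is worth correcting because correction is cheap. The symptom items lack an itemised pre-dose record and Table 16 lacks a baseline visit. Half of the scheduled FOBT and laboratory checklist answers (448 of 896) have no scheduled test behind them. The plan is also inconsistent about FOBT at early termination. The count assumes 32 subjects who complete all four checklist days, no unscheduled tests and no replacements.

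The effect of the unmeasured answers is confined to the checklist outputs. Measured FOBT and laboratory values are summarised separately at the visits where they are taken, and the FOBT and laboratory stopping criteria in Section 8.13.2 refer to results, not to checklist ticks. Nor would Table 16 be blind to bleeding on Days 1 and 2, because hematemesis and hematochezia can be observed then and have their own rows.

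A reader might want to go further and put a probability on background symptoms triggering the stopping criterion for moderate AEs in the same SOC. The documents give no background rate for these symptoms, and moderate severity means interference with daily activities in subjects selected for good health, so no such figure can be supported.

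**What to change.** 1. Give the Appendix B symptom items once before dosing, at Day -1 intake or pre-dose on Day 1. Record severity for any item present, so that worsening can be judged. Add a checklist row to the schedule.
2. Class a checklist AE as new or worsened against that record, the rule Section 11.1.5 already applies to the Stool Consistency Questionnaire. Add the pre-dose visit to SAP Table 16 as baseline.
3. Ask the FOBT and laboratory items only at visits where they are measured, or add 'not done'. In Table 16, use the number tested as the denominator for these rows.
4. Reconcile the Early Termination column and the Section 8.13.1 list with the checklist and Table 16 on FOBT.
5. Align the Listing 12 visits with the visits actually collected.

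While Table 16 is open, two other mismatches with Appendix B should be reconciled: the shell gives a hemoglobin decrease of 20 g/dL against 2 g/dL in the protocol, and it has no row for change in stool color (melena).

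The cost is one extra single-page form per subject during confinement, a form revision, a schedule row and SAP shell edits. Sample size and the planned summary methods do not change.

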APPENDIX A: Table Shells

APPENDIX B: Figure Shells

APPENDIX C: Data Listing Shells

1 LIST OF ABBREVIATIONS

| Abbreviation | Definition |
|----------------------------|--|
| λ_z | Elimination rate constant |
| AE | Adverse event |
| ALT | Alanine aminotransferase |
| AST | Aspartate aminotransferase |
| AUC | Area under the plasma concentration-time curve |
| CI | Confidence interval |
| CL | Cutaneous leishmaniasis |
| C _{max} | Maximum observed plasma concentration |
| CrCl | Creatinine Clearance |
| CRF | Case report form |
| CV | Coefficient of variation |
| DSU | Drug Studies Unit |
| EDTA | Ethylendiaminetetraacetic acid |
| FDA | Food and Drug Administration |
| g | Grams |
| h | Hour |
| ICH | International Conference on Harmonization |
| ID | Identification |
| IND | Investigational New Drug |
| IPT | Integrated Product Team |
| IV | Intravenous |
| MedDRA | Medical Dictionary for Regulatory Activities |
| mg | Milligrams |
| mL | Milliliter |
| mm | Millimeter |
| ng | Nonograms |
| PK | Pharmacokinetic(s) |
| QA | Quality Assurance |
| SAE | Serious adverse event |
| SAP | Statistical Analysis Plan |
| SD | Standard Deviation |
| SOC | System, Organ, Class |
| t _{1/2} | Apparent terminal exponential half-life |
| T _{max} | Observed time of maximum plasma concentration |
| USCD | University of California San Diego |
| WBC | White Blood Cells |

2 INTRODUCTION

This statistical analysis plan (SAP) for Protocol No. KIND-2022-01, “A Phase 1a Randomized, Double-blind, Placebo-controlled, Single Site, Single Ascending Dose Study of the Safety, Tolerability, and Pharmacokinetics of Kindolor Tosylate in Healthy Adults” describes and expands upon the analytical plan presented in the protocol.

This document contains all planned analyses, reasons and justifications for these analyses for all study data. This plan also includes sample tables, figures, and listings that will be populated. The SAP will follow the International Conference on Harmonization of Technical Requirements for Registration of Pharmaceuticals for Human Use (ICH) Guidelines as indicated in Topic E3 (Structure and Content of Clinical Study Reports), Topic E8 (General Considerations for Clinical Trials) and Topic E9 (Statistical Principles for Clinical Trials). The structure and content of the SAP provides sufficient detail to meet the requirements identified by the FDA and ICH.

The following sources were used in preparation of this SAP:

- Protocol # KIND-2022-01, Protocol Version No.: 8.0; Version Date: 30 August 2024
- ICH Guidance Topics E9, E3 and E8

3 PROTOCOL SUMMARY

3.1 Study Objectives

Primary: The primary objective of the study is to determine the safety and maximum tolerated dose (MTD) of kindolor tosylate in healthy volunteers.

Secondary: The secondary objective of the study is to determine the PK of kindolor tosylate by quantitating kindolor levels in plasma across a range of doses in healthy volunteers.

3.2 Study Design

This is a Phase 1a, randomized, double-blind, single ascending dose study designed to assess the safety, tolerability, and PK of kindolor tosylate. Healthy male and female adults were screened for eligibility by medical history, physical examination including height and body weight, vital signs, 12-lead electrocardiogram (ECG), clinical laboratory tests (amylase, lipase, chemistry, hematology, and coagulation tests, medical urinalysis, and infectious disease screen), urine drug screen for drugs of abuse, fecal occult blood tests (FOBT), and medication use. Females will have a pregnancy test.

Using a dose escalating design, eligible subjects received randomly assigned enteric coated oral tablets of kindolor tosylate (100 mg and 300 mg strengths) or identically matched Placebo tablets in 4 cohorts of 8 subjects (6 kindolor tosylate subjects and 2 placebo subjects in each cohort). A sentinel cohort of 2 subjects (1 active and 1 placebo) were dosed and closely monitored for at least 24 hours prior to dosing the remaining 6 subjects in each successive cohort. Ascending doses of kindolor tosylate include 100 mg (1 x 100 mg tablet), 300 mg (1 x 300 mg tablet), 900 mg (3 x 300 mg tablet), and 1800 mg (6 x 300 mg tablet). The safety data for each completed cohort was reviewed by the UCSD Clinical and Translational Research Data and Safety Monitoring Board (DSMB) that recommend continuation to the next cohort or stopping the study due to safety concerns.

Eligible subjects received intake procedures at the UCSD Clinical and Translational Research Institute Phase I unit on Study Day -1 (the day before the start of dosing) and completed final

screening and baseline evaluations including baseline assessments. On Study Day 1, subjects received the study drug after an overnight fast (about 8 hours) with no food allowed until 4 hours after dosing. Study drug tablets were administered with 240 mL of water. Subjects remained in the unit for at least an additional 48-hours for safety assessments and blood collections to determine plasma levels of kindolor. Pre-dose assessments were conducted prior to administration of study drug on Study Day 1. Blood for PK will be collected ~ 15 minutes prior to dosing, then at 0.25, 0.5, 1, 1.5, 2, 4, 8, 12, 24, and 48 hours after dosing. Safety will be assessed by collecting adverse events (AEs), vital signs, physical examination, ECG, FOBT, Stool Consistency Questionnaire, GI Symptoms Checklist, and clinical laboratory tests (amylase, lipase, chemistry, hematology, coagulation tests, pregnancy tests, and urinalysis). AEs were assessed daily after the start of dosing, with closer evaluations in the 4-hour period after the start of dosing. Sitting (3 minutes) vital signs were taken during screening, at clinic check in, pre-dose, then at 15, 30, 60 minutes and 2, 4, 6, 12, 24, and 48 hours post dose. A 12-lead ECG will be obtained prior to dosing, then at 2, 6, 12, 24, and 48 hours post dose. When vital signs or ECG were scheduled at the same time as a PK blood draw, these assessments were performed before drawing any blood. The FOBT will be performed at screening, clinic intake on Day -1, pre-discharge on Day 3, and at follow-up on Day 7. Subjects returned for a final follow-up visit 7±2 days after discharge for a final safety assessment including vital signs, ECG, AEs, FOBT, Stool Consistency Questionnaire, GI Symptoms Checklist, and clinical laboratory tests.

